6.2.5 Follow-up Assessments

All subjects will have follow-up assessments irrespective whether they discontinue study interventions or are non-compliant with interventions or use off-protocol treatments.

Follow-up Assessment at End of Treatment (weeks 8-10 depending on whether subject had fMRI): A subject visit will be arranged by study personnel for the post-treatment (end of counseling/hypnotherapy session) assessments which should occur within 2 weeks of finishing the treatment sessions for those subjects not undergoing fMRI or within 3 weeks of finishing treatment for those who will also undergo a follow-up fMRI. Subjects may have urine and vaginal swab samples collected and stored for possible future analysis (For example, urine may be analyzed for biomarkers).

The assessments and visit will include

- Questionnaires; OABq-SF, ISI, PPBC, PISQ-12, CRADI-8, IBS Module, and IC questionnaire. Follow-up Expectation Question and Compliance Questionnaire
- Voiding Diary
- Subject feedback regarding study participation
- Confirm subject contact information (patient email address, mailing address, cell and landline phone numbers, name/address/phone number of friend or relative in event of difficulty contacting patient)
- Confirm arrangements for patient incentive payments and for follow-up in 6 months

6 month Follow-up (month 6) the Study Coordinator or her designee will arrange 6 month follow-up assessment visits for subjects. Although it is preferable to have an in-person visit, it is possible to have the visit performed via phone and mail. Patient reimbursements will be paid at the in-person visit. If the subject has a phone/mail visit arrangements for reimbursement will be made following completion of this visit. The follow-up assessment should be completed within 5-7 months of completion of hypnotherapy or pharmacotherapy sessions.

Final assessments & follow-up include

- Questionnaires; OABq-SF, ISI, PPBC, PISQ-12, CRADI-8, IBS Module and IC questionnaire. Follow-up Expectation Question and Compliance Questionnaire
- Voiding Diary
- Subject feedback regarding study participation
- Confirm subject contact information (patient email address, mailing address, cell and landline phone numbers, name/address/phone number of friend or relative in event of difficulty contacting patient)
- · Confirm arrangements for patient reimbursement and for follow-up at 12 months

6.2.6 Completion/Final Evaluation

12 month Follow-up (month 12) The Study Coordinator or her designee will arrange 12 month follow-up assessment visits for subjects. Although it is preferable to have an in-person visit, it is possible to have the visit performed via phone and mail. Patient reimbursements will be paid at the in-person visit. If the subject has a phone/mail visit arrangements for reimbursement will be made following completion of this visit. The follow-up assessment should be completed within 10-14 months of completion of hypnotherapy or pharmacotherapy sessions. These same evaluations will be needed for subjects who discontinue study interventions early. Potential reasons for early termination include events which results in distress to the subjects as a result of study participation (See Chapter 7 Safety and Chapter 8 Intervention Discontinuation) and follow-up for all subjects who discontinue interventions but are willing to continue to participate in the study will be the same as though who continue the interventions (12 months).

Final assessments & follow-up include

- Questionnaires; OABq-SF, ISI, PPBC, PISQ-12, CRADI-8, IBS Module and IC questionnaire. Follow-up Expectation Question and Compliance Questionnaire
- Voiding Diary
- Subject feedback regarding study participation
- Thank subjects for study participation

7. Safety Assessments

Potential complications of the study interventions will be tracked (as described subsequently) and include the following;

Hypnotherapy

- Severe emotional upset
- CD/digital recording use while performing activities requiring intense concentration (driving)

'False Memory Syndrome' and severe emotional upset--- Relevant background, management and modification of intervention or participant assessments: Although, in the 1980s 'false memory syndrome' was described with the use of hypnotherapy in child abuse survivors, the current practice of hypnotherapy uses a much different approach to this therapeutic application. Current practice includes open-ended lines of questioning as opposed to suggestive or leading lines of questioning utilized in the 1980s with these victims. Transformation of hypnotherapy practices has greatly decreased occurrence of false memory syndrome. Recently, the hypermnesia attributed to the hypnotic state has been rejected based on more rigorous research.²² Last, the use of hypnotherapy in this study is for UUI treatment and recall of emotionally traumatic events will not be part of the hypnotherapy protocol. Thus, serious risk to subjects undergoing hypnotherapy for UUI is negligible. If a subject reports severe emotional upset attributed to the sessions, her sessions will be terminated. In the unlikely event that >33% of study subjects report that they experience serious emotional upset from study participation the study will be suspended and a review will occur. If these events are found to be attributable to hypnotherapy, the study will continue to be suspended until the hypnotherapy protocol is re-evaluated and revised (see below). Serious emotional upset includes inability to work or events that would necessitate evaluation by a physician or care provider. It is highly unlikely that hypnotherapy would unmask or de-repress significant emotional upset (e.g. hysteria, uncontrollable anger or hostility) in subjects. The potential for this occurring will be minimized by excluding subjects with a history of schizophrenia or untreated bipolar disorder and by having the hypnotherapist guide the sessions and terminate sessions if subjects are beginning to show signs of undue duress during hypnotherapy. Although other hypnotherapy studies have not reported significant

emotional upset as a complication, we believe that it is prudent to prepare for this unlikely possibility. A report of a subject experiencing serious emotional upset from study participation will result in a meeting of the PIs and review of the issues surrounding its occurrence. The PIs and Study Coordinator will generate a report, assess whether it was preventable, and develop an action plan to prevent recurrence including protocol revision and this report will be given the DSMB. While this occurrence is very unlikely, we recognize that sporadic occurrence of emotional upset is possible in any setting. In the very unlikely event that a third of subjects complain of significant emotional upset, the study should be halted until the circumstances surrounding its occurrence are investigated in depth.

Use of CD/digital recording while performing activities requiring intense concentration (driving)--Management and modification of intervention or participant assessments: Hypnotherapy subjects will be clearly instructed to ONLY use their hypnotherapy home practice CD/digital recording when and where they are can pay full attention to the recording. They will clearly be instructed NOT to listen to the hypnotherapy CD/digital recording during activities which require their full attention; specifically the will be instructed NOT to drive and listen to the home hypnotherapy practice CD/digital recording. If it is found that subjects listen to the CD/digital recording while they are driving, the PIs and Study Coordinator will generate a report and develop an action plan including protocol revision which will be given to the DSMB.

Pharmacotherapy:

- Constipation
- Dry Eyes
- Dry mouth
- Dyspepsia or Nausea
- Urinary Hesitancy or Retention

Relevant background, management and modification of intervention or participant assessment for the above: Serious adverse events related to anticholinergic medications are rare, however mild side-effects are relatively common; these include dry mouth, constipation, dyspepsia or mild nausea, dry eyes, and change in urination such as urinary hesitancy, as reported in an AHRQ and Cochrane meta-analysis.^{38,54} Subjects in this proposal will be informed regarding potential side effects of medications, will keep medication logs and will regularly meet with a medication counselor to review these side effects. If symptoms such as dry mouth, dry eyes, dyspepsia or constipation occur, if the patient finds the minor side effects to be bothersome and wishes to change medications the original anti-cholinergic may be changed to the alternate long acting anti-cholinergic. If there is a greater degree of symptom severity (e.g. obstipation, nausea and vomiting, urinary retention) the medication will be discontinued. A clinic visit to the UNM Urogynecology Clinic will be arranged so that the subjects may be appropriately evaluated. If subjects report symptoms of concern to the medication counselor or other study personnel, subjects will be instructed to stop the medication and a clinic visit to the UNM Urogynecology Clinic will be arranged so that subjects may be appropriately evaluated. These measures will decrease the risk of harm from study participation. It is unlikely that these FDA approved, routinely prescribed medications will result in serious harm, but if significant events are reported, subjects will be evaluated and the PIs and Study Coordinator will generate a report and which will be distributed to the DSMB, HRPO (if meets HRPO reporting guidelines see 7.4) and NCCAM consistent with NCCAM policies (see 7.4). If the events are attributable to the medications, an action plan will be developed which may include protocol modification.

Bladder Catheterization

- Dysuria
- Hematuria
- Urinary Tract Infection

Relevant background, management and modification of intervention or participant assessment for the above: Subjects will have bladder catheters placed for their cystometric evaluation and those who participate in the fMRI portion of the study will also be catheterized to undergo bladder filling for the fMRI task. Cystometric evaluation is considered a routine standard of care procedure for women with urgency urinary incontinence. The risks of bladder catheterization, although unlikely, include dysuria, hematuria and urinary tract infection. A recent meta-analysis concluded that prophylactic antibiotics for complex bladder testing decreased significant bactiuria with few side-effects, with a reported range of bactiuria of 1-8% in the groups treated with antibiotic prophylaxis.⁴⁶To decrease infection risks of bladder catheterization during this study, prophylactic antibiotics will be given to all subjects prior to and the day of catheterization. Nitrofurantoin or Trimethoprim/Sulfamethoxazole will be administered prior to and the day of catheterization. Subjects allergic to these medications will be given appropriate alternate antibiotic prophylaxis. Prior to the procedure, the patient will be informed regarding the procedure protocol and potential discomforts and side-effects. Participants will be clearly informed of their right to withdraw from the study at any time. Catheterization will be performed using sterile technique by nursing staff whose standard practice is to perform this procedure. Additionally, subjects will have urine dipsticks checked at study entry and prior to bladder catheterization to ensure absence of urinary tract infections. Subjects noting persistent urinary tract infection symptoms following the tasks will have urine dipstick testing and a urine culture performed. Subjects with evidence of a urinary tract infection will be treated. UTI, hematuria and dysuria occurrence will be tracked and AEs reported to the DSMB. If these events occur in 10% or more subjects, the protocol will be reviewed and revised.

FMRI

- Claustrophobia and Anxiety
- Dysuria, Hematuria and Urinary Tract Infection due to catheterization
- Unexpected Abnormality on MRI

Relevant background, management and modification of intervention or participant assessment for the above: These risks are small as MRIs are commonly performed clinical procedures without significant risk and without radiation exposure. To avoid the claustrophobia and anxiety which may occur with fMRI performance, subjects will be screened to rule out a history of claustrophobia prior to the MRI. Since the MRI may cause claustrophobia and anxiety from loud noises made by the machine (despite the fact that the MRN ambient scanner noise is below the current recommended guidelines), a two-way intercom system and a video monitoring system will provide continual monitoring of the subject's condition. If discomfort or concern is expressed or detected, the experiment will be stopped and the subject will be given the option to discontinue at any time. This event will be recorded. Please refer to evaluation and approach to events which may be associated with bladder catheterization described above. If an unexpected significant brain abnormality is found on fMRI the subject will be referred to her primary physician or other appropriate physician to evaluate the abnormality/finding.

Any of the following

• Possible breach of confidentiality, stress, emotional distress and inconvenience:

Relevant background, management and modification of intervention or participant assessment for the above: These risks are possible with participation in any research study and will be minimized. In the unlikely circumstance that confidentiality is breeched potential embarrassment associated with the diagnosis of urgency urinary incontinence may occur. This risk will be minimized by assigning a study number to each participant upon entry into the study and with the other measures described previously under Section III: Confidentiality in the DSMP. The stress, emotional distress and inconvenience will be minimized by recruiting, enrolling, evaluating and treating subjects in a private setting (private clinic exam rooms and private consultative, administrative, research and practitioners offices). The patient will reassured that declining study participation will have no effect on their current or future clinical care. HIPAA consent will be signed in accordance with the UNMH HRPO (IRB) and the patient informed of the protections that HIPAA guarantees to the privacy of their health information. To further ensure the security of personal health information all data will be de-identified as described above. The database will be password protected and accessible only to research personnel. Only coded information will be entered into the database. All paper-based study subject folders will be kept in a locked cabinet in the Urogynecology research division administrative area. Therapies will be administered in a one on one setting. Appointments for therapy will be scheduled with efforts made to minimize inconvenience to the subject while maintaining study fidelity and completing counseling therapies within a two month window.

7.1 Specification of Safety Parameters

Events will be captured by research staff as described in the DSMB with particular attention to the following noted in the Frequency of Specific Events Table and are also explained in Section 7.4 and include;

1) potential breach of confidentiality 2) lack of adherence to functional MRI screening for metallic objects near MRI scanner or potential lack of adherence to pregnancy and UTI screening 3) request for MRI termination due to anxiety, claustrophobia while in the scanner 4) symptoms of dysuria, hematuria or urinary tract infections

associated with bladder catheterization 5) potential symptoms related to anticholinergic use such as severe nausea/vomiting or constipation, or inability to void 6) potential symptoms related to hypnotherapy sessions such severe emotional upset which interferes with subject functioning 7) failure of subjects to comply with hypnotherapy CD/audio-recording instructions regarding prohibition of driving while listening to the recordings

7.2 Methods and Timing for Assessing, Recording, and Analyzing Safety Parameters

See section 7.0 above. As noted previously, the Frequency of Specific Events Table will be used to record the more significant potential symptoms/side effects of the interventions noted above and are further explained in Section 7.4 as well.

7.3 Adverse Events and Serious Adverse Events

Definitions

An adverse event (AE) is any untoward medical occurrence in a subject during participation in the clinical study or with the use of the interventions being studied. An adverse finding can include a sign, symptom, abnormal assessment (laboratory test value, vital signs, electrocardiogram findings, etc.) or any combination of these. AEs will be recorded regardless of their relationship to the study intervention.

A Serious Adverse Event (SAE) is any untoward medical occurrence that results in death, is life threatening requires inpatient hospitalization or prolongation of existing hospitalization, results in persistent or significant disability/incapacity or congenital anomaly. Generally, an SAE can result in one or more of the following outcomes:

- Death
- A life-threatening event
- Inpatient hospitalization or prolongation of existing hospitalization
- A persistent or significant disability/incapacity
- A congenital anomaly or birth defect
- Important medical event based upon appropriate medical judgment

Classification of AE Severity

AEs will be labeled according to severity, which is based on their impact on the patient. An AE will be termed "mild" if it does not have a major impact on the patient, "moderate" if it causes the patient some minor inconvenience and "severe" if it causes a substantial disruption to the patient's well-being.

AE Attribution Scale

AEs will be categorized according to the likelihood that they are related to the study intervention. Specifically, they will be labeled definitely unrelated, possibly related, probably related or definitely related to the study intervention.

AE Guidelines Adverse events will be reported in a manner consistent with the UNM HRPO (Human Research Protections Office) and NCCAM policies (See below).

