Potential adverse effects of pharmacotherapy: Subjects randomized to pharmacotherapy will be instructed take a standard anticholinergic extended release dose (see above) for urgency incontinence. Subjects with major contraindications to anticholinergic medications will be excluded from study participation (see exclusion criteria). Serious adverse events related to anticholinergic medications are rare, however mild side-effects are relatively common; these include dry mouth, constipation, dyspepsia or mild nausea, dry eyes, and change in urination such as urinary hesitancy.^{38,54} Subjects in this proposal will be informed regarding potential side effects of medications, will keep medication logs and will regularly meet with a medication counselor to review these side effects. Minor side effects may include symptoms such as dry mouth, dry eyes or constipation. The original anticholinergic may be changed to a different long acting anti-cholinergic for UUI if the patient finds the minor side effects to be bothersome and wishes to change medications. Serious medication related adverse events occur the medication will be discontinued (see protection against risks below). If subjects report urinary retention or other symptoms of concern to the medication counselor, subjects will be instructed to stop the medication. Simultaneously a clinic visit to the UNM Urogynecology Clinic will be arranged so that subjects may be appropriately evaluated. These measures will decrease the risk of harm from study participation.

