7.4 Reporting Procedures

Monitoring of Adverse Events & Frequency of Periodic Observations & Reporting & Follow-up: Adverse events will be monitored by spontaneous subject report and subject interviews and data review. At each clinic visit or follow-up telephone call, subjects will be asked to recall any adverse events since the time of their last contact (either via phone call, in-person clinic or study visit). The Study Coordinator (or her surrogate in her absence) will record the information using a standardized format and report the data to the PI's. If the AE is a reportable event as defined by the UNM HRPO (i.e. meets all the following criteria; it was unanticipated, caused harm or placed a person at increased risk of harm, and was more likely than not to have been related to the research) it will also be reported to the UNM HRPO (see UNM HRPO "Event form" attached which must be signed by the DSMB. The UNM HRPO will be notified of reportable events as soon as possible and within 5 days of the event date or

the "site awareness" date. AEs will be followed until they are resolved or considered stable, typically for one month, although this time will be extended to up to 4-6 months, depending on the instability of the event.

SAEs will be immediately (i.e. as soon as the Investigators or Study personnel are made aware that an SAE occurred) reported to the UNM IRB (HRPO) as per IRB guidelines and the NIH Project Officer and addressed by the DSMB if determined to be attributable to study participation (see SAEs below).

A Data Safety and Monitoring Board has been identified for this study. AE reports will be generated using standard forms, including the Adverse Event Case Report Form and Serious Adverse Event Case Report Form (see attached). The DSMB will meet quarterly for the first year and the DSMB will reassess and determine whether observations can be reviewed semi-annually thereafter. During the DSMP formal meetings the events will be reviewed. The severity of the event will be determined and an action plan to avoid recurrence of events (if found to be attributable to study participation) will be formulated and implemented. Research related adverse events will be reviewed and annual reports which include AE reports, subject enrollment/withdrawals and protocol violations will be generated for the University of New Mexico Health Sciences Center Human Research Protections Office (HRPO), Data Safety Monitoring Board and NCCAM/NCCAM Project Officer.

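### In section 7.3 the 'mild' and 'moderate' adverse event grades overlap and are out of order, so the mild/moderate split in AE reports cannot be relied on

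*Combined protocol and SAP*

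**What the plan says.** The classification in section 7.3 has a single axis: "AEs will be labeled according to severity, which is based on their impact on the patient". It then gives three definitions:

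- For the two lower grades, an event is "mild' if it does not have a major impact on the patient, 'moderate' if it causes the patient some minor inconvenience".
- For the top grade, an event is "severe' if it causes a substantial disruption to the patient's well-being".

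Serious adverse events have their own outcome-based definition in the same section, separate from these grades.

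Section 7, on pharmacotherapy, says that "mild side-effects are relatively common; these include dry mouth, constipation, dyspepsia or mild nausea, dry eyes". Section 5.1 describes the same kind of event with a different word: "Minor side effects may include symptoms such as dry mouth, dry eyes or constipation". Both sections add that a patient who is bothered by such effects may change to the other study drug.

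Section 7.4 has the Study Coordinator record AEs in a standardized format and report them to the principal investigators. In describing the formal review meetings it says: "The severity of the event will be determined and an action plan to avoid recurrence of events". It gives no further grading criteria.

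**The concern.** A severity scale should place each event in one grade and should rise as events get worse. The wording in section 7.3 does neither at its lower end. Two people who apply the text correctly can grade the same dry mouth differently, and a more troublesome event can be filed under the lower grade.

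What is at stake is the description of tolerability in AE reports. The harms that the plan expects most often fall at the faulty boundary. The plan's case for an alternative to medication also leans partly on poor tolerability of the drugs (sections 2.1 and 2.2). Anyone who reads a count of mild and moderate events, including the DSMB, would not know what the two columns separate.

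**Working it through.** The plan states no figure on this point, and none is needed. The check applies the three definitions of section 7.3 to rising levels of impact.

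| Impact of the event | Meets 'mild' (no major impact)? | Meets 'moderate' (minor inconvenience)? | Meets 'severe' (substantial disruption)? | Result |
|---|---|---|---|---|
| None noticed | Yes | No | No | Mild |
| Minor inconvenience | Yes | Yes | No | Mild and moderate |
| More than minor inconvenience, short of a major impact | Yes | No | No | Mild only |
| Substantial disruption | No, if this counts as a major impact | No | Yes | Severe |

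The second row shows the overlap. 'Mild' sets only an upper limit, and that limit lies above the level that defines 'moderate', so the moderate grade sits wholly inside the mild one.

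Comparing the second and third rows shows the wrong order. The lesser event may be called moderate, while the greater one can only be called mild.

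The fourth row assumes that a substantial disruption is a major impact. The text does not say so, but it is the natural reading, and under it 'severe' stays distinct from the two lower grades.

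The common drug effects land in the second row by the plan's own vocabulary. Section 7 calls them mild. Sections 5.1 and 7 also call them minor, and 'minor' is the word that defines the moderate grade. No other supplied section gives criteria that would settle the matter.

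The last step is to see which decisions use the faulty boundary:

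- Stopping the drug depends on named symptoms (sections 7 and 8).
- Severe emotional upset has its own description (sections 7, 8 and 9.4).
- Catheter-related events are reviewed on a 10% occurrence count (section 7).
- The statistical stopping comparison uses SAEs (section 9.4).
- Early unblinding refers to severe AEs (section 9.2).
- Section 9.6 plans no comparison by AE grade, and AE severity is not an outcome in sections 9.1 or 9.5.

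None of these turns on the line between mild and moderate. What remains affected is the grade recorded and reported for non-serious events below 'severe'.

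**The case against.** The strongest reply is that little depends on the defect. That stands: no rule or planned analysis in the supplied documents uses the mild/moderate boundary, and event type, count and attribution can be reported without it. The plan's own habit of calling the common anticholinergic effects mild also suggests how staff would label them in practice. It does not make the definition workable, because the same effects are called minor as well.

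The AE case report form, the Manual of Procedures and the data and safety monitoring plan are cited but not supplied, and they may hold clearer criteria. If they do, section 7.3 still conflicts with them and should point to them.

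Four stronger readings are tempting and are not supported:

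- A reader might infer that intermediate events have no grade. They have one, which is mild. A true gap would need 'major impact' to begin below 'substantial disruption', and the text does not say that.
- A reader might infer that the severity of drug side effects as a whole is uninterpretable. Only the mild/moderate split is.
- A reader might infer biased grading between arms, because different staff run the treatment visits. Section 7.4 has the coordinator record AEs and places the determination of severity in the context of the formal meetings. Nothing says that the hypnotherapist or the medication counselor assigns the grade.
- A reader might want a numerical swing. With 152 / 2 = 76 women per arm and an assumed 30% (range 20% to 50%) of drug-arm women having such an event, 0.30 × 76 = 23 women (0.20 × 76 = 15 to 0.50 × 76 = 38) could be counted as all mild or all moderate. That incidence is not in the documents, and the swing requires every event to be graded the same way, so it is an outer bound and not an estimate.

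**Conclusion.** The point holds in limited form, as an error in the wording and not merely missing detail. As written, every event that causes minor inconvenience qualifies for two grades, and events between that level and a major impact are graded below it. The mild/moderate split of non-serious AEs cannot be reliably interpreted.

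The consequence is minor and confined to AE reporting. The conclusion that 'severe' events are untouched rests on reading a substantial disruption as a major impact. The conclusion that nothing repairs the scale rests on the supplied text alone, without the AE form, the Manual of Procedures or the monitoring plan.

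**What to change.** Reword the lower two grades in section 7.3 so that the three exclude one another and increase in impact:

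- Mild: no more than minor inconvenience.
- Moderate: more than minor inconvenience, but not a substantial disruption to the patient's well-being.
- Severe: unchanged.

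Use the same wording on the AE form. Section 11.2 says that enrollment is complete, so AEs may already have been graded under the present text. Re-grade the recorded non-serious events from their descriptions before the blind is broken (section 9.2 sets that after 12-month follow-up and data checking). Hide the arm where possible, and state in the report that masking is imperfect, since a description such as dry mouth can reveal the arm.

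The cost is a short change to the protocol and the AE form, plus a brief re-grading by current staff. It alters a measurement definition only and leaves every treatment, discontinuation and stopping rule as it is.
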